8.2.2.1 Definition

Time to first Clinically Meaningful Response of $\geq 50 \times 10^9/L$: time from starting treatment to achievement of first response of $\geq 50 \times 10^9/L$ (computed as time from starting treatment to achievement of first response of $\geq 50 \times 10^9/L$. Date of first clinically meaningful response - Date of first treatment + 1)

The visit date when the first clinically meaningful response was recorded will be considered as the date of first clinically meaningful response.

8.2.2.2 Estimand's attributes

This secondary efficacy endpoint will be analyzed using the RS, under the same treatment conditions and population as for the primary endpoint while using the ICE, ICES described in Table 8-3 and the population level summary described below:

Table 8-3: Intercurrent Events (ICE), Intercurrent Events Strategies (ICES) and Missing data Strategies for the analysis of Time to first Clinically Meaningful Response of $\geq 50 \times 10^9/L$

Intercurrent Events (ICE)	ICE Strategy	Missing data strategy
a) Use of rescue therapy prior to Week 25	A while on-treatment strategy: For participants impacted by any of the ICE (a, b and c). Impacted data will be excluded from the time at risk.	Available platelet data up to the start date of this ICE will be utilized in statistical analysis.
b) Withdrawal from the study due to treatment emergent AE		
c) Permanent treatment discontinuation		
d) COVID-19*	Composite Strategy: data impacted by COVID-19 will	Section 4.2.2

Intercurrent Events (ICE)	ICE Strategy	Missing data strategy
	be excluded from the time at risk.	

* COVID-19 Impact category: Temporary discontinuation of study drug, Permanent discontinuation of study drug, Termination of study participation and Relationship to COVID-19: confirmed, suspected, general or other as recorded in the COVID-19 impact eCRF form.

Population-level summary: Owing to early termination of the study, the population-level summary will be provided using descriptive statistics. Median time to event will be estimated as median of observed values and also using the Kaplan-Meier estimate.

8.2.3 Clinically Meaningful Platelet Response by Day 8, defined as platelet count $\geq 50 \times 10^9/L$

This secondary efficacy endpoint will be analyzed using the RS, under the same treatment conditions and population as for the primary endpoint while using the ICE/ICES described in Table 8-4 and the population level summary described below:

Table 8-4: Intercurrent Events (ICE), Intercurrent Events Strategies (ICES) and Missing data Strategies for the analysis of Clinically Meaningful Response by Day 8

Intercurrent Events (ICE)	ICE Strategy	Missing data strategy
a) Use of rescue therapy up to Day 8	Composite strategy: Participants impacted by any of these ICE will be considered as non-responders.	Participants with missing data due to any of these ICE will be considered as non-responders.
b) TEAEs leading to permanent treatment discontinuation		
c) Discontinue prior to receiving IMP		
d) Study participant do not have a post-treatment assessment up to day 8		
e) COVID-19*	Composite Strategy: Participants impacted by ICE (e) will be considered as non-responders at the time of event.	Section 4.2.2

* COVID-19 Impact category: Temporary discontinuation of study drug, Permanent discontinuation of study drug, Termination of study participation and Relationship to COVID-19: confirmed, suspected, general or other as recorded in the COVID-19 impact eCRF form.

Population-level summary: Owing to early termination of the study, the population-level summary will be provided using descriptive statistics.

8.2.4 Response defined as platelet count $\geq 30 \times 10^9/L$ and at least a 2-fold increase of the Baseline count confirmed on at least 2 separate occasions at two adjacent nominal visits at least 7 days apart, and absence of bleeding

Definitions:

- a) Two adjacent nominal visits are defined as on-site visits where ITP bleeding scale assessment is performed

- b) Absence of bleeding indicated by Grade 0 for all domains of the SMOG, or a Skin Grade of 0 or 1 by visit

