Data from study TP0001 indicate that rozanolixizumab was tolerated with an acceptable safety profile after multiple (4mg/kg, 7mg/kg, and 10mg/kg) and single (15mg/kg and 20mg/kg) doses. The most frequent AE was headache (mild to moderate in intensity) and no severe headache was reported. There were no TEAEs leading to IMP discontinuation. Four serious TEAEs were reported overall (none were considered to be treatment-related by the investigator and were related to the underlying disease). A dose-dependent decrease in total IgG was observed: 43.6% (range 21.9% to 68.6%) for the 4mg/kg group (~Day 29), 49.9% (range 29.5% to 65.5%) for the 7mg/kg group (~Day 22), 63.8% (range 38.4% to 75.0%) for the 10mg/kg group (~Day 15), and on Day 8, after a single dose, for the 15mg/kg and 20mg/kg groups 52.3% (range 30.1% to 68.0%) and 60.2% (range 51.8% to 65.4%), respectively. Responders were classified as having a clinically relevant platelet response ($\geq 50 \times 10^9/L$). Five (35.7%) participants in the 4mg/kg and 7mg/kg groups, 5 (45.5%) of 11 participants in the 10mg/kg group, 8 (66.7%) of 12 participants in the single administration 15mg/kg dose group, and 6 (54.5%) of 12 participants in the single administration 20mg/kg group were clinically relevant responders.

Based on the above, UCB considers that TP0001 established supportive evidence of efficacy and safety and is proceeding with the development of rozanolixizumab for the treatment of adults with persistent or chronic primary ITP. UCB is proposing a clinical development Phase 3 program in this orphan disease population comprised of two placebo-controlled, confirmatory maintenance treatment efficacy and safety studies, TP0003 and TP0006, and a one-year long-term safety, OLE study, TP0004.

The current study, TP0003, will assess the efficacy, safety, and tolerability of rozanolixizumab administered as a fixed-unit dose equivalent to [REDACTED] QW via sc infusion in adult study participants with persistent or chronic primary ITP.

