Platelet Count	Secondary/MCP	Cumulative number of weeks with Clinically Meaningful Platelet Response of $\geq 50 \times 10^9/L$ over the 24-week treatment period	RS who were randomized to rozanolixizumab weekly dosing compared against those who received placebo.	A composite endpoint will be used where, in the case rescue therapy are taken, only the platelet data up to the start date of rescue therapy will be utilized for the statistical analysis. Participants who take rescue therapy or who are withdrawn owing to TEAEs are defined as having a loss of durable platelet response at the time of the event occurring.	Cumulative number of weeks with clinically meaningful platelet response will be analyzed using an analysis of covariance with fixed terms for treatment, splenectomy, degree of thrombocytopenia (platelet count < or $\geq 15 \times 10^9/L$). Estimated means and 95% CI will be presented for each treatment group.
Platelet Count	Secondary/MCP	Time to first Clinically Meaningful Platelet Response of $\geq 50 \times 10^9/L$: time from starting treatment to achievement of first response of $\geq 50 \times 10^9/L$	RS who were randomized to rozanolixizumab weekly dosing compared against those who received placebo.	A composite strategy will be used where, in the case rescue therapy are taken, only the platelet data up to the start date of rescue therapy will be utilized for the statistical analysis. Participants who take rescue therapy or who are withdrawn due to TEAEs are defined as having a loss of clinically meaningful platelet response and will be censored at the time of the event.	Time to first Clinically Meaningful Response will be analyzed using a stratified Log Rank Test with fixed terms for treatment, splenectomy, degree of thrombocytopenia (platelet count < or $\geq 15 \times 10^9/L$). Estimated hazard ratios and 95% CIs will be presented. The time to first Clinically Meaningful Response will

Objective Clinical Category	Statistical Category	Estimand			
		Variable/Endpoint	Population	IES ^a	PLS ^b (Analysis)
					be presented graphically using a Kaplan-Meier curve.

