3 DATA ANALYSIS CONSIDERATIONS

3.1 General presentation of summaries and analyses

Statistical analysis and generation of tables, figures, participant data listings, and statistical output will be performed using SAS® Version 9.4 or higher (SAS Institute, Cary, NC, USA).

All tables and listings will use Courier New font size 9.

Descriptive statistics will be displayed to provide an overview of the study results. For continuous variables, descriptive statistics will include number of participants with available measurements (n), mean, standard deviation (SD), the median, minimum, and maximum.

For categorical variables, the number and percentage of participants in each category will be presented. Unless otherwise noted, the denominator for percentages will be based on the number of participants included in the respective analysis set. Participants with missing data can generally be accounted for using the following approaches:

-
- For summaries of demographics and Baseline characteristics: summarize percentages based on all participants in the analysis set and include a “Missing” category (corresponding to participants with missing data for the variable being summarized) as the last row in the list of categories being summarized.
 - For summaries of efficacy and safety variables, unless otherwise specified: summarize percentages based only on those participants with observed data for the variable being summarized. As the denominator may be different from the number of participants in the analysis set being considered, the denominator should be displayed in the table. The general format for displaying this will be “n/Nsub (%)”

Unless otherwise noted, all percentages will be displayed to one decimal place. No percentage will be displayed for zero counts, and no decimal will be presented when the percentage is 100%.

For the purpose of the tabulations the lower and upper confidence limits for the percentages will be truncated at 0 and 100% respectively.

For PK concentrations, summary statistics will include geometric mean, geometric coefficient of variation (CV), 95% confidence intervals (CIs) for geometric mean, arithmetic mean, SD, median, minimum, and maximum. All summaries of PK variables will be based on the observed values. No imputation will be used.

Decimal places for descriptive statistics will always apply the following rules:

- “n” will be an integer
- Mean, SD, and median will use one additional decimal place compared to the original data

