- CV [%] will be presented with one decimal place
- Minimum and maximum will have the same number of decimal places as the original value.

If no participants have data at a given time point, for example, then only n=0 will be presented. However, if n<3, present the n, minimum and maximum only. If n=3, n, mean, median, minimum and maximum will be presented only. The other descriptive statistics will be left blank.

Derived variables in general will display the mean, SD and median to 1 more decimal place than the variables used in the derivation. If the number of decimal places reported in the raw data is varied, then use either the maximum raw number of reported decimal places or 3, whichever is the lowest, as a guide for the descriptive statistics.

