8.2.5.1 Estimand’s attributes

The same considerations for treatment conditions and population of interest as mentioned in items 1 and 2 in Section 8.1.1, except the endpoint which is described above and the following approach for ICE (see Table 8-5) and the population level summary:

Table 8-5: Intercurrent Events (ICE), Intercurrent Events Strategies (ICES) and Missing data Strategies for the analysis of Time to first rescue therapy

Intercurrent Events (ICE)	ICE Strategy	Missing data strategy
a) Withdrawal from the study due to TEAE	A composite strategy: Participants will be considered censored at the time of the ICE.	Not applicable
b) COVID-19*	A composite strategy:	Section 4.2.2

* COVID-19 Impact category: Temporary discontinuation of study drug, Permanent discontinuation of study drug, Termination of study participation and Relationship to COVID-19: confirmed, suspected, general or other as recorded in the COVID-19 impact eCRF form.

Population level summary: Endpoint will be descriptively summarized. Median time to event will be estimated using the Kaplan-Meier estimate.

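### Time to first platelet response: on its natural reading, the observed-value median in SAP 8.2.2.2 covers responders only and should not be labelled a median time to event

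*SAP*

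**What the plan says.** SAP 8.2.2.1 computes the time in days as "Date of first clinically meaningful response - Date of first treatment + 1". A participant who never responds has no such date, and nothing in Section 8.2.2 gives that participant a time.

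SAP 8.2.2.2 analyses the endpoint on the Randomized Set. Table 8-3 takes follow-up affected by rescue therapy, withdrawal for an adverse event, permanent discontinuation or COVID-19 out of the time at risk. The population-level summary is to use descriptive statistics, and then: "Median time to event will be estimated as median of observed values and also using the Kaplan-Meier estimate".

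SAP 3.1 sets the default for continuous variables: n (those with a measurement available), mean, SD, median, minimum and maximum. It adds: "However, if n<3, present the n, minimum and maximum only".

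Two other places bear on the point:

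- **Time to first rescue therapy.** SAP 8.2.5 says when participants without the event are censored, and for the median SAP 8.2.5.1 says only: "Median time to event will be estimated using the Kaplan-Meier estimate".
- **Protocol Table 9-2**, for time to first response: "Time to first Clinically Meaningful Response will be analyzed using a stratified Log Rank Test with fixed terms for treatment". A Kaplan-Meier curve is also planned there, but no median of observed values.

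**The concern.** Two numbers will carry one label. One respects censoring. The other, on the natural reading, selects participants by the outcome being timed: whoever never responds drops out of it. An arm in which fewer than half respond has no median time to response, yet a finite early day would be printed for it. With formal testing dropped (SAP 3.9), the descriptive tables are the efficacy result, so a mislabelled summary matters more than it would beside a formal analysis.

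**Working it through.** The SAP states no figure for this median, so there is nothing to reproduce.

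**Inputs**

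- Randomized: 33 (SAP 2.3). Allocation was 2:1. The actual split is not given; 22:11 is assumed.
- Response on rozanolixizumab: TP0001 reported 35.7% to 66.7% across dose groups (Protocol 2.2). It was an open-label study with one to five doses, so it serves only as a range.
- Response on placebo: Protocol 6.2.1.1 mentions a platelet increase in up to 10%.
- No intercurrent events, and non-responders followed to Week 25 (assumed).

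**Step 1: what the responders-only median estimates.** Let p be the responder share and F the distribution of response times among responders. The proportion of the whole arm that has responded by time t is p·F(t). At the responders' median F = 0.5, so the arm stands at p/2. The arm's own median needs p·F(t) = 0.5, that is F(t) = 1/(2p).

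- p = 0.60: the responders' median is the 30th percentile of the arm. The arm's median lies at 1/1.2 = 83% of the responder times.
- p = 0.45: the responders' median is the 22.5th percentile. 1/0.9 exceeds 1, so the arm has no median.

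This needs no assumption about how fast responders respond. If the share changes while F stays the same, the responders' median does not move.

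**Step 2: how often the two numbers part in an arm of 22.** Let X be the number responding, Binomial(22, p). The Kaplan-Meier curve ends at 1 − X/22. Counting a curve at or below 0.5 as having reached its median, it is not reached when X ≤ 10. The observed median is printed when X ≥ 3.

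| Response p | Arm quantile p/2 | P(X ≤ 10): Kaplan-Meier median not reached | P(X ≥ 3): observed median printed |
|---|---|---|---|
| 35.7% | 17.9% | 88% | 99.5% |
| 45% | 22.5% | 60% | over 99.9% |
| 54.5% | 27.3% | 26% | over 99.9% |
| 60% | 30% | 12% | over 99.9% |
| 66.7% | 33.4% | 3% | over 99.9% |

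An invented example: of 22, six respond on Day 8, three on Day 15, one on Day 29, and twelve never. The observed median over the ten responders is Day 8. The Kaplan-Meier curve ends at 12/22 = 0.545, so its median is not reached.

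**Step 3: the other reading.** Suppose the observed values include censored times counted as if they were responses. In the same example the median is Day 169, which is the length of follow-up and not a response time. In a simulation at 45% response with 30% censored early (assumed exponential response times among responders, mean 28 days), this reading gave about Day 82. The Kaplan-Meier median was not reached in 65% of runs.

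**Step 4: the placebo arm.** With 11 on placebo and 10% response, the probability of fewer than three responders is 0.314 + 0.384 + 0.213 = 0.910 (for 0, 1 and 2). The placebo observed median is then suppressed in about 91% of trials. At an assumed 20% the figure is 62%.

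**The case against.** The strongest reply is that little can go wrong. The Kaplan-Meier median is named in the same sentence. n is already required, so n = 10 beside an arm of 22 shows that 12 are missing from the observed median. Every participant is listed (SAP 8), and no inference is planned (SAP 3.9 and 4.7). All of this stands, and it limits the point to labelling.

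A second reply is that the SAP does not define an observed value, and that its wording on time at risk could give every treated participant a time. The ambiguity is real. It does not rescue the number, because that reading fails too (Step 3).

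Three stronger points are tempting, and the documents do not support them.

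- A reader might infer that the SAP breaks its own rule that "the denominator should be displayed in the table". That rule concerns percentages of categorical variables. For a continuous time SAP 3.1 asks for n, which will be shown.
- A reader might treat time to first rescue as a clean Kaplan-Meier-only precedent. SAP 8.2.5.1 also asks for a descriptive summary, so the default statistics could appear there as well. The contrast shows only which median the SAP names.
- A reader might see an unexplained departure from the protocol's censored-data analysis. SAP 3.9 openly replaces the formal efficacy analyses with description, and the Kaplan-Meier estimate is kept.

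**Conclusion.** The point holds as a labelling error in a descriptive summary. On the natural reading, one of the two numbers called a median time to event is a summary of responders, and it lies too early in the arm's distribution. The p/2 result rests on complete follow-up alone. The percentages rest also on the assumed 22:11 split and on no intercurrent events.

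A reader might go further and infer that the table will make placebo look as fast as rozanolixizumab. At the placebo rate the protocol mentions, the placebo observed median will usually not be printed. Higher placebo rates are assumptions.

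Nor can a size in days be given. Response speed is not in the documents, the schedule in Protocol Table 1-4 has a Day 3 platelet count as well as the weekly ones, and the 33 participants followed earlier schedules (SAP 3.2.1). Any day value is an illustration. Severity is the lowest grade.

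**What to change.** Replace the sentence in SAP 8.2.2.2 with text to this effect: *The median time to event is the Kaplan-Meier estimate, shown as not reached where that applies. Any other descriptive statistics of observed times, including the default mean and median of Section 3.1, are labelled 'among responders, n/N' in each arm and are not used to compare arms.*

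Deleting the phrase about observed values is not enough. The sentence before it still calls for descriptive statistics, and the Section 3.1 defaults would print a responders-only mean and median again.

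Optionally, state the censoring date for participants who never respond and have none of events (a) to (c) in Table 8-3, as SAP 8.2.5 does for rescue therapy. The last platelet count up to Week 25 would serve. Table 8-3 itself stays unchanged.

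The cost is one sentence, one table label and one optional clarification. No new data are needed.

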Platelet Count	Secondary/MCP	Clinically Meaningful Response by Day 8, defined as: platelet count $\geq 50 \times 10^9/L$	RS who were randomized to rozanolixizumab weekly dosing compared against those who received placebo	A composite strategy will be used for rescue therapy, ie, participants who require rescue therapy will be considered a non-responder. The same strategy will be used for TEAEs leading to treatment discontinuation, and participants who discontinue prior to receiving IMP, do not have a valid Baseline assessment or do not have a post-treatment assessment.	To test of the null hypothesis (H_0) in participants who have achieved a Clinically Meaningful Response by Day 8, defined as: Platelet count $\geq 50 \times 10^9/L$ that the true common odds ratio between treatment arms is 1 (odds ratio = 1) vs the alternative hypothesis (H_a) that the odds ratio is less than 1, a Cochran-Mantel Haenszel model adjusted for the stratification factors, namely baseline degree of thrombocytopenia (platelet count $<$ or $\geq 15 \times 10^9/L$), history of splenectomy (yes or no).
Platelet Count	Secondary/MCP	Response defined as platelet count $\geq 30 \times 10^9/L$ and at least a 2-fold increase of the Baseline count confirmed on at least 2 separate	RS who were randomized to rozanolixizumab weekly dosing	A composite strategy as described for Clinically Meaningful Response by Day 8 will be used.	To test of the null hypothesis (H_0) in participants who have achieved a Response by Day 8, defined as: Platelet count $\geq 30 \times 10^9/L$ and at least a 2-fold increase of the Baseline count, confirmed

		Estimand			
Objective Clinical Category	Statistical Category	Variable/Endpoint	Population	IES ^a	PLS ^b (Analysis)
		occasions at two adjacent nominal visits at least 7 days apart, and absence of bleeding.	compared against those who received placebo		on at least 2 separate occasions at two nominal visits at least 7 days apart, and absence of bleeding, that the true common odds ratio between treatment arms is 1 (odds ratio = 1) vs the alternative hypothesis (H _a) that the odds ratio is less than 1, a Cochran-Mantel Haenszel model adjusted for the stratification factors, namely baseline degree of thrombocytopenia (platelet count < or ≥15×10 ⁹ /L), history of splenectomy (yes or no).

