8.1 Statistical analysis of the primary efficacy endpoint

8.1.1 Primary analysis of the primary efficacy endpoint

The primary efficacy endpoint will be analyzed according to the following estimands' attributes:

- (1) Treatment conditions: Placebo and rozanolixizumab (please refer to section 6 Study treatments in the protocol for details)
- (2) Population: Adult Study Participants with Persistent or Chronic Primary Immune Thrombocytopenia (ITP) who fulfill the inclusion / exclusion criteria according to the protocol.
- (3) Endpoint: Durable Clinically Meaningful Platelet Response of $\geq 50 \times 10^9/L$, for at least 8 out of 12 weeks during the last 12 weeks (Week 13 to Week 25)
This endpoint includes the platelet count recorded at Week 14 to Week 25 corresponding to the response achieved following dosing at Week 13 to Week 24)
- (4) Intercurrent Events: see below.

Table 8-1: Intercurrent Events (ICE), Intercurrent Events Strategies (ICES) and Missing data Strategies for the analysis of the primary endpoint

Intercurrent Events (ICE)	ICE Strategy	Missing data strategy
a) Use of Rescue therapy from Baseline prior Week 25	A composite strategy Participants impacted by any ICE (a, b, c and d) will be considered as non-responders after the time of event.	Not applicable Section 4.2.2
b) Participants who experience any TEAEs leading to permanent treatment discontinuation		
c) Participants who discontinue prior to receiving IMP		
d) Participants who do not have any post-treatment assessment		
e) COVID-19*	A composite strategy Participants impacted by ICE (e) will be considered as non-responders at the time of event.	

* COVID-19 Impact category: Temporary discontinuation of study drug, Permanent discontinuation of study drug, Termination of study participation and Relationship to COVID-19: confirmed, suspected, general or other as recorded in the COVID-19 impact eCRF form.

(5) Population-level summary: Owing to early termination of the study, the population-level summary will be provided using descriptive statistics.

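### SAP Table 8-4 puts no Day 8 limit on discontinuation for a TEAE, so, read as written, a participant who responded by Day 8 and stopped later is scored a Day 8 non-responder

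*SAP*

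**What the plan says.** SAP 8.2.3 covers a binary secondary endpoint, "Clinically Meaningful Platelet Response by Day 8, defined as platelet count" of at least 50 × 10⁹/L, summarized descriptively on the Randomized Set. Table 8-4 lists its intercurrent events. Two of them end at Day 8: "a) Use of rescue therapy up to Day 8" and "d) Study participant do not have a post-treatment assessment up to day 8". Row c, stopping before any IMP is given, needs no limit. Row b reads "b) TEAEs leading to permanent treatment discontinuation" and has none.

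Rows a to d share one rule: "Composite strategy: Participants impacted by any of these ICE will be considered as non-responders". The COVID-19 row is worded differently: "Participants impacted by ICE (e) will be considered as non-responders at the time of event".

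Protocol Table 9-2, in the Day 8 row, says "participants who require rescue therapy will be considered a non-responder. The same strategy will be used for TEAEs leading to treatment discontinuation". It gives no date limit for either event.

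**The concern.** Whether a participant responded by Day 8 is settled once the Day 8 window closes. An event after that cannot change what was observed. Row b, joined to a rule that acts on the whole participant, lets a discontinuation many weeks later overwrite an early response already on record.

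What is at stake is the meaning of the reported figure. The table would be labelled as a Day 8 response rate. It would in fact give the proportion who responded by Day 8 and never afterwards stopped for a TEAE. It could also disagree with other tables in the same report that rest on the same platelet counts.

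**Working it through.** The documents state no expected rate or power for this endpoint, so there is no plan figure to reproduce. The check has three parts: a comparison of the rules, a worked case, and an illustration of size.

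**1. The rules for a TEAE discontinuation, side by side**

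| Place | Endpoint | Time element |
|---|---|---|
| SAP Table 8-1 | Durable response (primary) | Non-responder after the event |
| SAP Table 8-2 | Cumulative weeks of response | Platelet data used up to the event |
| SAP Table 8-3 | Time to first response | Platelet data used up to the event |
| SAP Table 8-4, row b | Response by Day 8 | None |
| Protocol Table 9-2 | Response by Day 8 | None |

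The wording for the primary endpoint is "Participants impacted by any ICE (a, b, c and d) will be considered as non-responders after the time of event". Table 8-4 lacks that closing qualifier for rows a to d. SAP 4.2.1 and 4.2.2 set no Day 8 cut-off that would supply it.

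**2. One participant followed through the tables**

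Take a participant with a count of at least 50 × 10⁹/L on Day 8 who stops IMP for a TEAE at Week 20.

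- Table 8-3: the first response is on Day 8, before the event, so it counts.
- Table 8-2: that week is credited.
- Table 8-4: row b applies, so the participant is a non-responder by Day 8.

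The same count is a response in two tables and not in the third.

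The window for this is long. SAP 2.3 notes that the analysed cohort was dosed every two weeks until Week 23. Week 23 is Day 155 in the protocol's schedule of activities. 155 − 8 = 147 days, or 21 weeks after Day 8.

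**3. Size**

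Inputs: 33 randomized and a planned 2:1 allocation (SAP 2.3). The actual split is not given. I assume 22 on rozanolixizumab and 11 on placebo.

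- One re-scored rozanolixizumab participant: 1/22 = 4.5 percentage points.
- One re-scored placebo participant: 1/11 = 9.1 percentage points.

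Let p be the true Day 8 response rate in an arm and d the share of Day 8 responders who later stop for a TEAE. The rate as scored is p × (1 − d), a loss of p × d. Both p and d are assumed.

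| p | d = 0.05 | d = 0.10 | d = 0.20 |
|---|---|---|---|
| 0.30 | 1.5 points lost | 3.0 | 6.0 |
| 0.45 | 2.25 | 4.5 | 9.0 |
| 0.60 | 3.0 | 6.0 | 12.0 |

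In a 22-participant arm this is 22 × 0.30 × 0.05 = 0.33 to 22 × 0.60 × 0.20 = 2.64 participants. Row b can turn a responder into a non-responder but never the reverse, so the loss has one direction within each arm.

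**The case against.** The best defence is SAP 4.2.1, which treats efficacy data that are missing because of a TEAE discontinuation as the intercurrent event. A participant with a recorded Day 8 count has no missing Day 8 value, so a later stop might not qualify. The missing-data column of Table 8-4 also speaks of data missing because of these events. Since two neighbouring rows end at Day 8, the gap in row b looks like an oversight that a programmer might correct unprompted. This makes a softer reading possible. It does not remove the problem: Table 8-4 handles missing data in a separate column, its strategy column acts on the event itself, and no text sets a Day 8 cut-off for row b.

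The objection that little hangs on the result stands. SAP 3.9 and 4.7 remove formal efficacy testing and multiplicity control, so no test or ranking is affected. SAP 8 has all efficacy variables listed by treatment group and visit, so the observed Day 8 counts remain visible.

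A reader might infer that the rule biases the comparison against rozanolixizumab, because stops for TEAEs would be commoner on active drug. The documents do not support that. Protocol 2.2 reports no TEAE leading to IMP discontinuation in TP0001, no discontinuation for TEAEs in UP0018, and similar TEAE incidence between arms in CIDP01 apart from injection or infusion site reactions. Those studies do not rule it out either: UP0018 gave single doses and TP0001 at most five. Protocol 7.1.3 requires permanent discontinuation for serious or recurrent severe headache or GI disturbance related to IMP, but also for life-threatening bleeding, which can occur on placebo.

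**Conclusion.** The point holds as a defect in the stated scoring rule. Followed as written, Table 8-4 gives a wrong Day 8 status to any Day 8 responder who later stops for a TEAE, and it conflicts with Tables 8-2 and 8-3.

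The effect is about 4.5 points per affected rozanolixizumab participant and 9.1 per affected placebo participant, given the assumed 22/11 split. The 1.5 to 12 point range is an illustration over assumed p and d. The number affected is not in the documents and could be zero. Each arm's rate can only fall, but the direction of any difference between arms is unknown. It would also go too far to say that participants have been mis-scored, since the documents do not show how the derivation was programmed.

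Because the endpoint is a descriptive summary in 33 participants of a terminated study, this is a correction worth making for the accuracy of the report. It does not threaten a trial conclusion.

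**What to change.** - In SAP Table 8-4, add *on or before Day 8* to row b. Alternatively, state under the table that events after Day 8 do not change Day 8 status. Say which date decides, so that the derivation is unambiguous.
- Give SAP 8.2.4.1 its own event window, for example non-responder at visits after the event. That section takes over the 8.2.3 considerations for the by-visit Response endpoint, where a Day 8 limit does not fit. Amending row b alone would carry the limit across and leave later TEAE discontinuations unaddressed there. The Day 8 limits on rescue and missing assessment are already inherited in this way.
- If the protocol is reissued, align the Day 8 and Response rows of Table 9-2. The Day 8 row needs the limit for rescue as well as for TEAE discontinuation, and the Response row should stop borrowing its strategy. As no one was randomized under Amendment 3, the SAP change is the one that matters.

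The cost is a phrase in Table 8-4, a few lines in 8.2.4.1 in place of the cross-reference, and one date condition in each derivation. No new data are needed: dosing dates and AE details are already listed under SAP 10.1 and 10.2.
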